Email: [contact]

[name]
Children's Hospital Colorado
[name]
Aurora, CO 80045
[contact]
[contact]
Email:
[contact]

[name]
The University of North Carolina at Chapel Hill
[name]
Chapel Hill, North Carolina
Office: [contact]
[contact]
Email:[contact]

IND SPONSOR AND MEDICAL MONITOR

[name]
Dana-Farber Cancer Institute
[name]
Boston, MA 02215
[contact]
[contact]
Email: [contact]

ABSTRACT

¹³¹I-Metaiodobenzylguanidine (¹³¹I-MIBG) is one of the most active agents for patients with relapsed or refractory neuroblastoma. A large multicenter phase 2 study yielded an estimated overall response rate in this population of 36% using single-agent ¹³¹I-MIBG. Recent NANT clinical trials have demonstrated the feasibility of combining ¹³¹I-MIBG with systemic radiation sensitizers, with the aim of enhancing the antitumor activity of ¹³¹I-MIBG.

NANT 04-06 was a phase 1 dose escalation study of ¹³¹I-MIBG together with vincristine and protracted irinotecan (20 mg/m²/day IV x 5 days x 2 weeks) as a radiation sensitizer. This combination was tolerable using ¹³¹I-MIBG doses up to 18 mCi/kg. However, more patients than anticipated from either drug alone developed protocol-associated diarrhea, a known toxicity of protracted irinotecan exposures. Furthermore, the new national standard shown to be effective in other tumor types has been a 5-day higher dose irinotecan schedule. Therefore, a pilot study at UCSF evaluated ¹³¹I-MIBG together with vincristine and irinotecan given at higher doses for a shorter exposure (50 mg/m²/day IV x 5 days x 1 week). This study confirmed that vincristine and irinotecan could be safely combined with ¹³¹I-MIBG up to doses of 18 mCi/kg, with lower rates of diarrhea compared to NANT 04-06. Promising antitumor activity was seen in both studies of this combination.

NANT07-03 was a phase 1 dose escalation study of ¹³¹I-MIBG together with vorinostat, an oral histone deacetylase (HDAC) inhibitor. The rationale for this study included three main points. First, vorinostat has modest activity against neuroblastoma in preclinical models. Second, vorinostat has been shown to sensitize tumor cells, including neuroblastoma, to the effects of radiation therapy. Third, vorinostat upregulates the expression of the norepinephrine transporter on neuroblastoma cell lines. This phase 1 study demonstrated that 14 days of vorinostat could safely be combined with ¹³¹I-MIBG up to doses of 18 mCi/kg.

While these combination trials have demonstrated promising antitumor activity, these small phase 1 studies have not clarified whether combination therapy results in increased response rates compared with single-agent ¹³¹I-MIBG. The current randomized phase 2 pick the winner study is therefore designed to select the ¹³¹I-MIBG treatment regimen associated with the highest objective response rate. Patients with relapsed or refractory neuroblastoma and MIBG-avid disease will be randomized at study entry to one of three treatment arms: single-agent ¹³¹I-MIBG; ¹³¹I-MIBG with vincristine and irinotecan; and ¹³¹I-MIBG with vorinostat. All patients will receive 18 mCi/kg ¹³¹I-MIBG with prophylactic autologous stem cell support two weeks following ¹³¹I-MIBG infusion. Patients enrolling prior to Amendment 7A may receive up to two courses of therapy. Patients enrolling with Amendment 7A and after may receive only one course of therapy. The primary endpoint is objective response following the first course of therapy, using standard NANT response criteria. Secondary and other endpoints will include toxicity, site specific response, best response for patients treated with two courses of therapy (if applicable), overall survival, and correlative biology endpoints related to radiation exposure. Up to a total of 105 eligible and evaluable patients will be randomized to one of the three arms.

[figure not shown]
Hypothesis:

We hypothesize that:

- ¹³¹I-MIBG, combined with either vorinostat or irinotecan, will be associated with a higher objective response rate compared with single-agent ¹³¹I-MIBG;
- ¹³¹I-MIBG, combined with either vorinostat or irinotecan, will be tolerable but associated with an increase in protocol-associated toxicity compared with single-agent ¹³¹I-MIBG;
- ¹³¹I-MIBG, combined with either vorinostat or irinotecan, will be associated with increased measures of radiation exposure as assessed by peripheral blood markers.

TREATMENT SCHEMA

Patients will be randomized at study entry to one of three treatment arms.

Patients assigned to single-agent ^{131}I -MIBG (Arm A) will receive 18 mCi/kg ^{131}I -MIBG on Day 1 and autologous stem cell infusion on Day 15.

Patients randomized to receive vincristine / irinotecan / ^{131}I -MIBG (Arm B) will receive vincristine 2 mg/m² (maximum dose 2 mg; see 4.2.2.1 for dosing if < 3 years old) intravenously on Day 0. They will receive irinotecan 50 mg/m² (maximum dose 100 mg) intravenously on Days 0 to 4. Patients will also receive diarrhea prophylaxis with cefixime 8 mg/kg/day orally on Days -1 to +6. Patients will receive 18 mCi/kg ^{131}I -MIBG on Day 1 and autologous stem cell infusion on Day 15.

Patients randomized to receive vorinostat / ^{131}I -MIBG (Arm C) will receive vorinostat orally once daily on Days -1 to +12 (14 total doses) at a dose of 180 mg/m² (maximum dose 400 mg). Patients will receive 18 mCi/kg ^{131}I -MIBG on Day 1 and autologous stem cell infusion on Day 15.

All patients will undergo disease restaging between Day 43 and 50, 6-7 weeks after ^{131}I -MIBG infusion. Patients enrolling prior to Amendment 7A with at least stable disease after the first cycle can receive a second cycle of therapy, provided they meet specified protocol criteria.

1.0 GOALS AND OBJECTIVES (SCIENTIFIC AIMS)

Primary Aim:

1.1

To identify the ^{131}I -MIBG treatment regimen associated with the highest overall response rate after one course of treatment on the following three arms: single-agent ^{131}I -MIBG; vincristine / irinotecan / ^{131}I -MIBG; or vorinostat / ^{131}I -MIBG

Secondary Aim:

1.2

To compare the toxicity profiles associated with each of the following three ^{131}I -MIBG treatment regimens: single-agent ^{131}I -MIBG; vincristine / irinotecan / ^{131}I -MIBG; or vorinostat / ^{131}I -MIBG

Exploratory Aims:

1.3

To describe best overall response for patients treated with two courses of therapy, site-specific response of bone marrow, soft tissue, and MIBG-avid lesions as well as overall survival and progression-free survival following each of three ^{131}I -MIBG treatment regimens

1.4

To assess peripheral blood and bone marrow minimal residual disease at study entry and following each of three ^{131}I -MIBG treatment regimens quantified using a neuroblastoma-specific NB 5-gene detection assay (NB5 assay) by TaqMan[®] low density array (TLDA)

1.5

To compare whole body radiation exposure in patients with neuroblastoma treated with each of three ^{131}I -MIBG treatment regimens

1.6

To evaluate peripheral blood lymphocyte γ -H2AX foci levels, expression of a panel of DNA damage response genes in peripheral blood mononuclear cells, plasma Flt-3 ligand, serum amylase, and circulating tumor DNA as markers of radiation exposure, response, and toxicity in patients with neuroblastoma treated with each of three ^{131}I -MIBG treatment regimens

1.7

To evaluate the performance of a computerized MIBG scan scoring system in patients with relapsed or refractory neuroblastoma treated with ^{131}I -MIBG therapy

1.8

To evaluate the association between tumor norepinephrine transporter (NET) protein expression and response to protocol therapy.

1.9

To describe the concordance rate between institutional Curie score and centrally reviewed Curie score in patients with relapsed or refractory neuroblastoma.

1.10

To describe the incidence and severity of sinusoidal obstruction syndrome (SOS) in patients with neuroblastoma who receive ^{131}I -MIBG therapy on this protocol and subsequently receive high-dose chemotherapy with stem cell rescue as part of their clinical care.

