4.6 Criteria to Receive a Second Course of Therapy

Patients who meet all of the following criteria at the end of the first course of therapy may proceed to a second course of assigned therapy:

- Enrolled prior to Amendment 7A (patients enrolling with Amendment 7A and later may receive a single course only);
- Adequate stem cells to support a second course per section 3.2.6;
- Organ function meets criteria in section 3.2.10 except:
 - EKG only needs to be repeated prior to course 2 for patients randomized to vorinostat arm; all arms require repeat echocardiogram); and
 - Platelets only need to recover to $\geq 25,000/\mu\text{L}$ (no transfusions for one week prior to CBC documenting platelet recovery to this level);
- No intervening anti-cancer therapy between first course and planned second course;
- Day 1 of planned second course no earlier than Day 43 of first course (minimum 6 weeks between ^{131}I -MIBG infusions);
- No delayed engraftment (section 4.7) or need for dose modification (section 4.8) in first course of therapy;
- Disease status at end of first course of stable disease or better (section 11)
- Cumulative lifetime assigned dose of ^{131}I -MIBG does not exceed 36 mCi/kg at time of planned second infusion on this protocol (based upon assigned dose during that prior therapy; to account for unavoidable dose rounding, maximum previously delivered dose must not exceed 38 mCi/kg).

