4.8.2 Irinotecan Dose Modifications

For patients who develop grade 3 diarrhea persisting more than 72 hours with appropriate therapy or any grade 4 diarrhea during the five-day course of irinotecan, the remaining doses of irinotecan should be omitted for the course.

4.9 **Concomitant Therapy**

4.9.1 No other cancer chemotherapy, radiotherapy, biologic therapy, or immunomodulating agents will be used.

4.9.2 Appropriate antibiotics, blood products, anti-emetics, fluids, electrolytes and general supportive care are to be used as necessary (see also Section 5.0).

4.9.3 No medications that interfere with ¹³¹I-MIBG uptake should be given during the week prior or after ¹³¹I-MIBG therapy (see Appendix V).

4.9.4 Patients randomized to receive vorinostat may not receive valproic acid until disease re-evaluation following the last planned course of therapy has been completed.

4.9.5 Patients receiving vorinostat have rarely had QT prolongation.¹¹⁰ A formal QT study was performed in which patients with advanced cancer received a single supratherapeutic dose of vorinostat of 800 mg or placebo.¹¹⁰ No patients had QT_c prolongation of more than 30 msec and no patients had QT_c > 480 msec. The effect of vorinostat with other drugs that prolong the QT interval is not clear, though no issues were noted on NANT07-03 with vorinostat, ¹³¹I-MIBG, and allowed use of ondansetron. Patients assigned to the vorinostat arm may not receive other medications known to prolong the QT_c interval within 1 week prior to or 1 week following vorinostat (Appendix II; note that this list prohibits the use of pentamidine and cautions investigators with the use of ondansetron).

4.9.6 Vorinostat treatment may result in mild increases in serum creatinine. Caution should be exercised with the use of nephrotoxic medications while patients are receiving vorinostat.

- 4.9.7 The following agents that may interfere with irinotecan metabolism may not be administered to patients assigned to the irinotecan arm until Day 15 of the second course of protocol therapy:
- High-dose dexamethasone (other systemic corticosteroids allowed only for management of asthma, allergy, premedication for blood transfusions, or management of CNS lesions);
 - Aprepitant (Emend);
 - Ketoconazole and St. John's Wort;
 - Phenobarbital, carbamazepine, phenytoin.

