10.3.2 Primary Response Endpoint and Additional Assessments of Treatment Effect

The primary endpoint and analysis will be objective tumor response after one course of therapy based on central review, for all eligible randomized patients who received any amount of ¹³¹I-MIBG (modified intent-to-treat analysis). Two secondary analyses will (a) include all eligible randomized patients and (b) only patients evaluable for response as defined in the paragraph above in section 10.3.1. Patients will undergo complete disease staging (¹²³I-MIBG diagnostic scan, bilateral bone marrow aspirate and biopsy, anatomic imaging with CT or MRI scan, and urine catecholamines) at baseline and then approximately 6 weeks following ¹³¹I-MIBG infusion. Response will be assessed according to NANT response criteria v1.1. These criteria are modified from the International Neuroblastoma Response Criteria¹¹² in that they utilize RECIST 1.1 criteria for measurable tumors¹¹³ and Curie score for MIBG scan response.¹⁰⁶ Patients with an institutional report of complete response, complete response-MRD, partial response, or stable disease will have their response centrally reviewed. An exact logistic regression analysis will be used to compare the 3 arms in terms of response, while controlling for the stratification variables.

For the subset of patients receiving a second course of therapy (enrolled prior to Amendment 7A), the response to the second course of therapy will be reported as well as the overall response to two courses of protocol therapy. Response to the first course will nevertheless be the primary endpoint for study.

Additional endpoints for response to treatment will include response at each site of disease: bone marrow; soft-tissue sites; and ¹²³I-MIBG using NANT response criteria. Progression-free survival and overall survival (summarized with Kaplan-Meier plots) will be additional secondary endpoints.

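### Best response to two courses is described only in patients selected on first-course outcome, so the subset rate is not comparable between arms and is expected to run high

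*Combined protocol and SAP*

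**What the plan says.** Aim 1.3, under the exploratory aims, begins "To describe best overall response for patients treated with two courses of therapy" and ends by tying its list of outcomes to each of the three regimens. The Abstract repeats the restriction among the secondary and other endpoints: "best response for patients treated with two courses of therapy (if applicable". Section 10.3.2 says that, for patients who had a second course, "the response to the second course of therapy will be reported as well as the overall response to two courses of protocol therapy".

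Section 4.6 decides who is in that group. A patient who meets every criterion "may proceed to a second course of assigned therapy", so course 2 is optional. Three of the criteria matter here:

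- Enrolment period: "Enrolled prior to Amendment 7A (patients enrolling with Amendment 7A and later may receive a single course only".
- Disease status: "Disease status at end of first course of stable disease or better (section 11".
- Tolerance: "No delayed engraftment (section 4.7) or need for dose modification (section 4.8) in first course of therapy".

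The section 4.8 cited in the last criterion holds rules for vorinostat (4.8.1) and irinotecan (4.8.2, for example "the remaining doses of irinotecan should be omitted for the course"). It holds none for 131I-MIBG given alone.

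First-course response is handled differently. Section 10.3.1 counts progression, early death and inevaluable status as non-response, and the primary population is every eligible randomized patient given any 131I-MIBG. No section plans best response over everyone enrolled before Amendment 7A. None cautions against comparing the two-course subset between arms.

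**The concern.** Membership of the two-course group is settled by what happened in course 1, and one of the conditions is itself a category of the response scale. A patient who progresses, dies early or cannot be assessed after course 1 is a certain non-responder, yet drops out of the denominator. A first-course responder who goes on stays in both numerator and denominator.

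The selection also need not act alike across arms. First-course progression may differ by regimen, and the dose-modification criterion has a defined trigger only in Arms B and C. The protocol's own hypothesis is that the combinations will be more toxic than 131I-MIBG alone, so uneven selection can be foreseen.

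Aim 1.3 refers to each of the three regimens, so the natural product is three rates side by side. A reader would take them as what up to two courses of each regimen achieve in the patients assigned to it. They do not measure that.

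**Working it through.** **The plan's own figures.** The plan states no figure for the two-course endpoint. Its nearest figure is the 80% chance of selecting the best arm with 35 per arm and a 15-point advantage (section 10.5). An exact binomial calculation for three arms, at the least favourable rate and requiring a strict win, gives 79.4%, so that figure reproduces. It concerns first-course response, and nothing below alters it.

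**Inputs.**
- R, first-course response rate: 36% (single-agent phase 2 figure in the Abstract and section 2.2) or 20% (prior mean in Appendix VIII).
- f, share barred from course 2 as non-responders: not in the documents; assumed 10% to 50%.
- q, share of first-course stable patients who convert to response in course 2: not in the documents; assumed 0 or 10%.
- Uptake of course 2 among those who qualify: not in the documents; first taken as unrelated to response.

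**Step 1: size.** With stable share S = 1 - R - f, the subset rate is (R + qS)/(1 - f). With q = 0 this is R/(1 - f).

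| R | f = 10% | 20% | 30% | 40% | 50% |
|---|---|---|---|---|---|
| 20% | 22.2% | 25.0% | 28.6% | 33.3% | 40.0% |
| 36% | 40.0% | 45.0% | 51.4% | 60.0% | 72.0% |

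With q = 0, a denominator of all treated patients returns R itself.

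**Step 2: ranking.** With equal q in both arms, the weaker arm overtakes when f_weak > 1 - R_weak × (1 - f_best)/R_best. Taking f_best = 10%:
- 20% versus 25%: 1 - 0.20 × 0.90/0.25 = 28%
- 20% versus 30%: 1 - 0.20 × 0.90/0.30 = 40%
- 20% versus 35%: 1 - 0.20 × 0.90/0.35 = 49%

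Illustration with q = 10% and all non-progressors going on. An arm with R = 30%, f = 40% gives (0.30 + 0.10 × 0.30)/0.60 = 55%. An arm with R = 36%, f = 20% gives (0.36 + 0.10 × 0.44)/0.80 = 50.5%. Over all patients the rates are 33% and 40.4%, in the opposite order.

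**Step 3: chance.** Take true rates of 20/22/25% with 40/25/15% barred. The subset rates are 33.3/29.3/29.4%. By simulation with an assumed 6 to 12 two-course patients per arm, the weakest arm shows the highest observed rate 39% to 42% of the time, against 25% to 28% with the same numbers and no selection.

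**Step 4: if uptake depends on response.** Let u_R and u_S be uptake among first-course responders and stable patients. Counting course-1 response only, the subset rate is R·u_R/(R·u_R + S·u_S). It equals R when u_R/u_S = S/(1 - R). At R = 36%, that ratio is 0.44/0.64 = 0.69 for f = 20%, and 0.24/0.64 = 0.38 for f = 40%. Below those ratios the subset rate falls under R.

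**Step 5: dose modification.** Removing dose-modified patients raises an arm's rate if they respond less often than the rest who would qualify, and lowers it if they respond more often. The documents do not say which. What is fixed is that the criterion can act through section 4.8 in Arms B and C only.

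**The case against.** The strongest reply is that this is an exploratory item worded as description. Aim 1.3 says describe, where Aims 1.2 and 1.5 say compare. Section 10.3.2 attaches no test, ranking or by-arm rate to the subset, and the exact logistic regression between arms belongs to the primary endpoint. First-course progressors are already counted as non-responders in that analysis, and progression-free and overall survival are also reported. Since Amendment 7A the protocol gives one course, so the subset describes an option no longer offered. Describing what happened to those who took it is a fair question. The progression shares and uptake are assumed, the reversal examples use convenient values, and groups of 6 to 12 could not support a ranking in any case.

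Most of this stands, and it limits the point to reporting. It does not remove it. Aim 1.3's closing reference to each regimen makes by-arm figures the likely output, and nothing tells the reader not to compare them. Nor is the cohort trivial. The first interim analysis, planned at 60 evaluable patients, reached the DSMB in March 2017, before Amendment 7A was dated in June 2017. If it was run at its planned size, about 60 of up to 105 patients entered while two courses were allowed.

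**Conclusion.** The point holds as a reporting weakness in an exploratory endpoint. The two-course rate is conditioned on post-randomization events and should not be compared between arms. If uptake is unrelated to response, it is expected to exceed the first-course rate by the factor 1/(1 - f): 36% becomes 45% to 60% for an assumed 20% to 40% barred, before any benefit from course 2.

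Three stronger readings might be inferred, and the documents support none of them.

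- That the trial could pick the wrong regimen or that its primary result is in doubt: selection rests on first-course response by central review, which is not conditioned on course 2.
- That the rate is certainly inflated in every arm: course 2 is optional, some patients are expected to go on to myeloablative therapy, and preferential departure of responders would shrink or reverse the excess.
- That excluding dose-modified patients raises the rates: that exclusion has no fixed direction and only makes the arms unlike.

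Reversal of the ranking is possible rather than shown. At the design difference of 15 points (20% versus 35%), it would need about 49% barred in the weaker arm against 10% in the better one. Small gaps reverse far more easily.

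**What to change.** In section 10.3.2, under Aim 1.3:

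1. Report best overall response by randomized arm in all eligible patients enrolled before Amendment 7A who received any 131I-MIBG, counting those who had one course at their course-1 response.
2. Beside it give, per arm, the number and share entering course 2 and the reasons the others did not.
3. Keep the two-course subset as a labelled descriptive listing, with a statement that it is not to be compared between arms.

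No treatment criterion in section 4.6 or 4.8 needs to change. The cost is a few lines of analysis text and one extra table. Restaging after each course is already required, so no new assessment is needed. The reported best-response figure will probably be less favourable.

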2.0 BACKGROUND

2.1 Neuroblastoma

Neuroblastoma is the most common extracranial solid cancer of childhood.¹ Most patients are initially diagnosed prior to 10 years of age. Approximately 50% of patients present with initially metastatic disease. Many of these patients are either refractory to initial therapy or develop recurrent disease after receiving multimodal therapy. The outcome for patients with recurrent or refractory disease remains poor. Novel approaches to treating these patients are required to improve their outcome.

2.2 ¹³¹I-MIBG: Clinical Data in Neuroblastoma

¹³¹I-metaiodobenzylguanidine (MIBG) is a guanethidine analog with specific uptake in sympathetic nervous system tissues. The norepinephrine transporter mediates uptake of ¹³¹I-MIBG into the cells of these tissues.² As a tumor derived from the sympathetic nervous system, neuroblastoma cells avidly accumulate ¹³¹I-MIBG.³⁻⁵ Low doses of both ¹³¹I-MIBG and ¹²³I-MIBG are widely used as nuclear medicine imaging agents in the diagnostic evaluation of patients with neuroblastoma.

Given that neuroblastoma is radiosensitive, high-dose ¹³¹I-MIBG has been evaluated as a targeted radiopharmaceutical in the treatment of patients with neuroblastoma for the past 25 years. Unlike standard external beam radiotherapy, ¹³¹I-MIBG is administered intravenously and then distributes throughout the body.⁶ The biological or effective half-life of the administered radiation in the blood of patients with neuroblastoma ranges from 9-130 hours, reflecting clearance mainly in the urine.⁶⁻⁸ Radiation that is not cleared in the urine or stool remains in the body and decays with a half-life of approximately 8 days, the physical half-life of ¹³¹I.⁹ Since ¹³¹I-MIBG taken up by neuroblastoma cells is not cleared in the urine or stool, these cells are exposed to radiation with a half-life that more closely follows the physical half-life of ¹³¹I. Therefore, three weeks following therapeutic ¹³¹I-MIBG administration, tumor cells may still be exposed to small amounts of radiation.

The whole body radiation dose received is approximately linear with ¹³¹I-MIBG dose administered. After a dose of 12 mCi/kg, patients receive a calculated whole-body radiation dose of approximately 2 Gy.¹⁰ As a targeted radiopharmaceutical, the dose delivered to the tumor is much higher.¹⁰

Aside from transient nausea and xerostomia, the main early toxicity of ¹³¹I-MIBG therapy is myelosuppression. With higher doses (> 12 mCi/kg ¹³¹I-MIBG), hematologic toxicity becomes dose-limiting and hematopoietic stem cell infusion has been used to promote hematologic recovery.¹¹ Thrombocytopenia occurs more often and is more prolonged than neutropenia, particularly for those patients with bone marrow disease prior to ¹³¹I-MIBG treatment.¹² In one study using 18 mCi/kg ¹³¹I-MIBG, the median time to platelet nadir was 24 days and patients who did not receive hematopoietic stem cell support required platelet transfusions for a median of 5 weeks.¹² Nonhematologic toxicity has been minimal, even at higher doses. In a phase I dose escalation study of ¹³¹I-MIBG, no grade 3 or 4 nonhematologic toxicities were observed following a single course of therapy.¹¹ In a phase II study in which patients received 18 mCi/kg ¹³¹I-MIBG, 22% of patients had a grade 3 non-hematologic toxicity and 9% of patients had a grade 4 non-hematologic toxicity.¹³ The majority of these toxicities consisted of febrile neutropenia and other infectious complications. Patients on these studies have been able to receive multiple courses of therapy without unanticipated toxicity.¹³⁻¹⁵ In one series, 28 patients received at least two courses of therapy with a median ¹³¹I-MIBG dose of 18 mCi/kg given at a median interval of 98 days between treatments.¹⁵ Of the 24 patients who received two courses of ¹³¹I-MIBG, only 8 patients received stem cell reinfusion to support hematologic recovery. Non-hematologic toxicity was as expected based upon patients treated with only one course of ¹³¹I-MIBG. Potential late toxicities include hypothyroidism, secondary malignancy, and reduced fertility.¹⁶⁻¹⁸

Early studies evaluated ¹³¹I-MIBG as monotherapy for patients with recurrent or refractory disease. The objective response rate in these studies ranged from 30% to 37%.^{11, 13, 14, 19} The response rate with monotherapy may be even higher in patients with newly diagnosed disease.^{20, 21} A recent large phase II trial demonstrated that ¹³¹I-MIBG is one of the most active agents in patients with progressive, relapsed, or refractory neuroblastoma.¹³ Of 164 patients, of whom 148 were treated with 18 mCi/kg, 36% had an objective response. Patients > 12 years of age and those with disease limited to either bone/bone marrow or soft tissue, but not both, were more likely to achieve response following ¹³¹I-MIBG as single-agent therapy. A more recent study has confirmed that older patients appear to have a higher response rate to ¹³¹I-MIBG.²²

The use of multiple ¹³¹I-MIBG treatments to higher cumulative doses has also been assessed. Multiple treatments of ¹³¹I-MIBG at 56 day intervals have been shown to be tolerable.²³ NANT protocol 2000-01 evaluated double infusion of ¹³¹I-MIBG given two weeks apart to cumulative doses of up to 42 mCi/kg, supported by PBSC infusion.²⁴ Doses of 18 mCi/kg x 2 doses (36 mCi/kg) were well-tolerated. Cumulative lifetime doses of 54 mCi/kg have also been used, mainly on compassionate access protocols. There have not been any late liver, renal, or cardiac toxicity in patients with multiple infusions. Recent studies from the Children's Hospital of Philadelphia have shown that ¹³¹I-MIBG can be given at 42 day intervals without increased toxicity.²⁵

Based on these encouraging results, the NANT consortium has conducted phase 1 trials evaluating ¹³¹I-MIBG in combination with radiation sensitizers (see below). In addition, the Children's Oncology Group has opened a pilot study incorporating ¹³¹I-MIBG therapy into the upfront treatment of children with high-risk neuroblastoma.

